7.1.5 Handling of Missing Data

Sensitivity analyses performed for a single variable are described in detail in the corresponding section below.

Data listings will include the observed values. For derived variables, values based on imputed data will be presented in listings.

7.1.6 Interim Analyses

No interim analysis is planned.

7.1.7 Multiplicity

Three hypotheses are specified in the Protocol, one primary and two secondary hypotheses. Time-to-resolution using the visit day at which resolution was first seen, will be considered statistically significant if the sum of the p-value for the primary variable and the p-value from the time-to-resolution analysis is less than the specified overall significant level. The use of a non-inferiority alternative if the difference alternative should not be obtained, does not affect the overall p-value level of the primary hypothesis.

Hypotheses tested for other secondary variables will all be analysed using significance elves of 0.05.

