7.6. Sample Size Determination

From the results of the sponsor's observational, case series retrospective study 038/SI, a CRR_12 of 67% for the conventional combination therapy of PHMB 0.02% and propamidine 0.1% is expected.²⁰ This figure is in the range of cure rates described in the literature.^{13,22,23} If the true

difference in CRR_12 is 0.20 (Δ) (or more) in favor of PHMB monotherapy (0.08% PHMB), a total sample size of 116 subjects (allowing for 10% loss to follow-up) should give the study at least 80% power to detect superiority, with 2-sided alpha=0.10 (or equivalently 1-sided alpha=0.05).

Assuming a prevalence of late stage disease, and worse outcomes, in 38% of subjects, the expected CRR_12 in the control group will be reduced from 67% to 63%. To account for the inclusion of this group, the sample size has been adjusted to 130 subjects (allowing for 10% loss to follow-up).

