7.1.1 Presentation of Results

All results will be presented for each visit by treatment group and in total, unless stated otherwise. It should be clearly stated which unit applies to each presented variable.

Continuous data will be summarised using descriptive statistics, and the following parameters will be reported:

- number of subjects with evaluable observations and missing observations
- arithmetic mean and change from baseline with standard deviations

LINK Medical Study ID: PSR012

- median
- first and third quartiles
- minimum and maximum

Categorical data will be presented using absolute frequency and percentage. When the absolute frequency is zero, the percentage will not be presented. Unless stated otherwise, the denominator for percentage calculations will be the total number of subjects in the applicable analysis set, including subjects with missing data. For variables with missing values, the number and percentage of subjects with missing values will be presented.

Significance tests will be two-sided and performed at the 5% significance level, unless stated otherwise. When reporting the results of significance tests, p-values will be presented.

All confidence intervals (CIs) presented will be two-sided with a nominal confidence level of 95%, unless stated otherwise.

Data will be presented using an appropriate number of decimal places, to ensure that undue precision is not implied (e.g. the number of decimals should not exceed the accuracy of the measuring instrument). Raw data will be presented with the same number of decimals as collected, and derived data with an appropriate number of decimals based on general practice, mathematical rationale or scientific rationale.

Minimum and maximum values will be presented with the same number of decimals as the analysed variable and the other descriptive statistics will be presented with one decimal more. Percentages and proportions will be presented with one decimal. Odds ratios and hazard ratios will be presented with 3 decimals, and small and large values will be presented as '<0.001' and '>999.999' respectively. CI bounds will be presented with the same number of decimals as the corresponding point estimate, and p-values will be presented with 4 decimals or as '<0.001'.

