7.9.3 Secondary Efficacy Variables¹

Time-to-cure comparison between the treatment groups is specified as efficacy hypothesis and will be subjected to formal statistical testing. Other analyses of secondary efficacy variables will be done on a hypothesis-generating basis, i.e. no p-value adjustments will be conducted, and conclusions regarding the analysis results will be commented on such a basis.

Time-to-cure

The aim of the hypothesis test is to show that the time is less among the subjects receiving PHBM 0.08% monotherapy compared to the comparator. Patients will either be classified as Cured at some point of time while in the study or leave the study without being classified as Cured. As a secondary efficacy variable, timeto-cure (clinical resolution) will be analysed. The Cox Proportional Hazards regression (subject to validity of the 'proportional hazards' assumption) and Kaplan-Meier survival plots. If the proportional hazard assumption is not fulfilled a logrank test will be performed. Not all patients may have information regarding when they were cured, e.g. due to death before being cured, or completed the study without being cured. Both the Cox Proportional Hazards regression and the Kaplan-Meier plot uses the censoring timepoint in their calculations. The censoring timepoint will be defined based on the timepoint of the last observation when cure status was assessed. The null hypothesis is that the two treatment arms have equal hazard functions. Relevant data will be presented at the Clean file meeting for discussion and acceptance.

BCVA

The VAMS states that: "Depending on the problem, this notation can be most useful when analysing or graphically plotting visual acuity scores because equal linear steps on the LogMAR scale represent equal ratios in the standard size sequence." Hence, BCVA will be presented and analysed using LogMAR values, where

$$LogMAR = \log \left(\frac{ORRES_{BCA2}}{ORRES_{BCA1}} \right),$$

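### The sum-of-p-values rule for time-to-cure is valid but needlessly conservative: fixed-sequence testing rejects whenever it does, at the same maximum family-wise error.

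*SAP*

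**What the plan says.** SAP 7.1.7 counts one primary and two secondary hypotheses. Time-to-resolution is significant "if the sum of the p-value for the primary variable and the p-value from the time-to-resolution analysis is less than" a threshold that is described only as "the specified overall significant level". The section gives no number for that level, no reason for adding p-values and no testing order. It adds that falling back on non-inferiority leaves the level of the primary hypothesis unaffected. All other secondary variables are tested at 0.05.

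SAP 7.9.3 says that the time-to-cure comparison "is specified as efficacy hypothesis and will be subjected to formal statistical testing". The other secondary efficacy analyses are hypothesis-generating. SAP 7.9.1 names the test for difference in CRR_12 as the primary test of efficacy.

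The documents give more than one level. Protocol 7.6, repeated in SAP 5.1, plans the trial at two-sided 0.10 (one-sided 0.05). SAP 7.1.1 sets a default: "Significance tests will be two-sided and performed at the 5% significance level, unless stated otherwise". The protocol has no multiplicity rule for time-to-cure.

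**The concern.** Adding the two p-values makes time-to-cure pay for however small or large the primary p-value is, even after the primary test has succeeded. With p = 0.03 for each test, the sum is 0.06 and time-to-cure fails at alpha 0.05. With p = 0.06 for each, the sum is 0.12 and it fails at alpha 0.10. In both cases the primary is significant, and a fixed sequence would let time-to-cure be tested at the full level and succeed.

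At stake is power for the only secondary efficacy comparison that is formally tested, in a rare-disease trial of 130 subjects. The primary test, its confidence interval and the non-inferiority conclusion are not affected.

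**Working it through.** **The plan's own figure.** Protocol 7.6 and SAP 5.1 give a difference of 0.20, two-sided alpha 0.10, 80% power and 10% loss. The unpooled formula is n per arm = [p1(1−p1) + p2(1−p2)] × (1.645 + 0.842)² / 0.20², using unrounded normal quantiles.

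- 67% vs 87%: (0.2211 + 0.1131) × 6.183 / 0.04 = 51.7, so 52 per arm and 104 evaluable. 104 / 0.9 = 115.6, so 116. This matches.
- 63% vs 83%: (0.2331 + 0.1411) × 6.183 / 0.04 = 57.8, so 58 per arm and 116 evaluable. 116 / 0.9 = 128.9, so 129, or 130 for equal arms. This matches.

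The documents state no power or error rate for the sum rule itself.

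**Nesting.** Let p1 be the primary p-value and p2 the time-to-cure p-value. Since both are at least 0, p1 + p2 < alpha implies p1 < alpha and p2 < alpha. In the unit square the sum region is a triangle of area alpha²/2 inside a fixed-sequence square of area alpha². This holds for any correlation, effect or alpha. No simulated case passed the sum rule and failed the fixed sequence.

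**Maximum error for the pair CRR_12 and time-to-cure.** Under both rules time-to-cure can be declared only if p1 < alpha.

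- Both nulls true: the family-wise error is P(p1 < alpha) = alpha under either rule.
- Very large primary effect and no time-to-cure effect: p1 is near 0, so both rules reduce to p2 < alpha. Simulation gave 0.050 for both at alpha 0.05 and 0.100 for both at alpha 0.10.

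**Power, equal-power grid.** These are 2,000,000 bivariate-normal draws per scenario with two-sided p-values and the same assumed power for each test. Entries are the percentage of draws in which time-to-cure is declared, sum rule / fixed sequence.

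| Alpha | Power of each test | Corr. 0 | Corr. 0.5 | Corr. 0.8 | Corr. 0.9 |
|---|---|---|---|---|---|
| 0.10 | 80% | 60.7 / 64.0 | 64.7 / 68.7 | 67.7 / 72.9 | 68.9 / 75.0 |
| 0.10 | 71% | 46.2 / 50.4 | 52.2 / 56.9 | 56.3 / 62.3 | 57.8 / 64.9 |
| 0.05 | 80% | 61.3 / 64.0 | 65.5 / 68.7 | 68.6 / 72.9 | 69.9 / 75.0 |
| 0.05 | 71% | 47.0 / 50.4 | 53.1 / 56.9 | 57.3 / 62.3 | 58.9 / 64.9 |

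At zero correlation the fixed-sequence entries are simply 0.80² = 0.640 and 0.71² = 0.504. The loss is 3.3 to 7.1 points at alpha 0.10 and about 3 to 6 at alpha 0.05.

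**Power at the design effect.** Under exponential cure times, 63% vs 83% by day 365 implies a hazard ratio of ln(0.17)/ln(0.37) = 1.78, with 58 × (0.63 + 0.83) = 85 cures. For correlations 0, 0.5 and 0.8:

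- Alpha 0.05: sum 48.7, 54.6, 58.5%; fixed sequence 52.0, 58.3, 63.2%.
- Alpha 0.10: sum 63.6, 67.2, 69.8%; fixed sequence 66.6, 70.9, 74.5%.

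With a hazard ratio of 1.5 the loss is 3.4 to 4.7 points.

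**Simulated trials.** There were 20,000 trials with 58 per arm, exponential cure times, 30-day visits to day 365, a z-test on the rate difference and a log-rank test. The two z-statistics correlated at about 0.9, because both endpoints come from the same resolution record (SAP 7.9.1). At 63% vs 83%:

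- Alpha 0.05: sum 60.8%, fixed sequence 66.9%.
- Alpha 0.10: sum 71.3%, fixed sequence 77.4%.

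The loss is 6.1 points at either alpha.

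**The case against.** The strongest defence is that the rule is pre-specified, valid and leaves the primary analysis alone, so the issue is efficiency and not error. That stands. A reader might infer that adding p-values inflates the type I error. It does not: the sum region lies inside a procedure that already controls the error.

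The rule also buys something. Only the maximum error is equal. With both nulls true, correlation 0.8 and alpha 0.10, time-to-cure is falsely declared in 3.2% of draws under the sum rule and about 5.0% under the fixed sequence. With the primary at its design effect, no time-to-cure effect, zero correlation and alpha 0.05, the figures are 2.7% and 3.4%. Control at alpha does not require this extra protection, but it is a real difference.

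A reader might also infer that a primary result favouring the comparator could help time-to-cure pass, since the rule adds two-sided p-values without a direction condition. In practice this is negligible. With both nulls true it occurred in none of 2,000,000 draws at correlation 0.8, and about once in 100,000 at correlation 0.5 and alpha 0.10. With true effects in opposite directions (z-means −1 and +1), correlation 0.8 and alpha 0.10, it was 0.03%. It reaches about 5% only with opposite effects and independent tests, which is implausible for two endpoints built on one record. Any two-sided gate has the same gap, and SAP 7.9.3 states the intended direction.

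Finally, 7.1.7 does not say which primary p-value enters the sum, so one might think that a non-inferiority result could carry time-to-cure and that a superiority gate would remove that route. SAP 7.9.1 points the other way, because it names the test for difference as the primary test. On that reading a p-value at or above alpha already blocks time-to-cure, and a superiority gate takes nothing away.

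**Conclusion.** The point holds as one of efficiency. The sum rule is valid but stricter than it needs to be. That fixed-sequence testing rejects whenever it does, with the same maximum family-wise error, is algebra and rests on no assumption.

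The size of the loss does rest on assumptions: 71 to 80% power for each test, correlation 0 to 0.9, and proportional hazards with exponential cure times and no early dropout among the 116 evaluable subjects in the simulated trials. Protocol 7.6 claims "at least 80% power to detect superiority" for CRR_12, and no document gives power for time-to-cure. Within those ranges the loss is about 3 to 7 points at alpha 0.10 and about 3 to 6 at alpha 0.05. The high correlation in the simulated trials puts the likely loss near 6.

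Both alphas are shown because 7.1.7 does not say which applies. The documents do not support treating 0.10 as the settled level for this rule.

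**What to change.** Replace the sentence in SAP 7.1.7 with:

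> If the primary test for difference in CRR_12 is significant at the overall two-sided level in favour of 0.08% PHMB, time-to-cure is tested at that same full level and in the same direction; otherwise, including when only non-inferiority is shown, it is descriptive.

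State the overall level in 7.1.7 as a number, and reconcile the two-sided 0.10 of Protocol 7.6 and SAP 5.1 with the 5% default in SAP 7.1.1. Without that number neither rule can be applied unambiguously.

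The cost is one sentence and one figure, with no new data, settled before the randomisation code is broken. The trade-off is a somewhat higher false-positive rate for time-to-cure away from the worst case, never above alpha. The direction condition is a tidy-up with negligible practical effect.

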5.1 Sample Size

A total of 130 subjects affected by *Acanthamoeba* keratitis will be assigned to one of the above two treatment groups in a ratio of 1:1.

The protocol states, in section 7.6:

"From the results of the sponsor's observational, case series retrospective study 038/SI, a CRR_12 of 67% for the conventional combination therapy of PHMB 0.02% and propamidine 0.1% is expected. This figure is in the range of cure rates described in the literature. If the true difference in CRR_12 is 0.20 (Δ) (or more) in favour of PHMB monotherapy (0.08% PHMB), a total sample size of 116 subjects (allowing for 10% loss to follow-up) should give the study at least 80% power to detect superiority, with 2-sided alpha=0.10 (or equivalently 1-sided alpha=0.05).

LINK Medical Study ID: PSR012

Assuming a prevalence of late stage disease, and worse outcomes, in 38% of subjects, the expected CRR_12 in the control group will be reduced from 67% to 63%. To account for the inclusion of this group, the sample size has been adjusted to 130 subjects (allowing for 10% loss to follow-up, i.e. 116 evaluable subjects).

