7.10.2 Adverse Events

AEs data will be captured and encoded by system organ class (SOC) and the lowest level term (Medical Dictionary for Regulatory Activities, current version). A listing of AEs will be created. This listing, at minimum, will contain a description of AEs as to seriousness, severity, onset date and end date, duration, action taken (if any), outcome and likelihood of drug causation ("relation"). A frequency table will be compiled for AEs by treatment group, SOC, and lowest level term. Frequency tables will be compiled showing the number of subjects per treatment group affected by one or more (related) AEs, including percentages, the total number of AEs per treatment group and the average number of AEs per subject exposed to the respective treatment for the following:

- AEs.
- Serious AEs.
- AEs leading to withdrawal of the IMP.
- Fatal AEs.
- AEs, broken down by severity.
- AEs, broken down by causality assessment.

There will also be tables on the most frequently reported AEs, on system organ class level and on preferred term level. The decision on the frequency cut-off for these tables will be taken during the analysis of the AEs data in consultation with the author of the clinical study report and could be influenced by factors such as the overall number of AEs, study design, and the nature of the indication. The frequency cut-off should be mentioned in a table note.

The second secondary hypothesis, as specified in the protocol, is that AEs, and those relating to toxicity in particular, are less with PHMB 0.08% monotherapy compared to the comparator. This translates into:

Hypothesis: Rate of AEs is equal in the PHMB 0.08% monotherapy is equal to that of the comparator. In particular:

Hypothesis: Rate of toxicity-related AEs is equal in the PHMB 0.08% monotherapy is equal to that of the comparator

The null hypothesis is that rate of occurrence of AEs and toxicity-related AEs are equal for the two treatment arms.

If these are rejected, the conclusion is that the rates are different, and less with PHMB 0.08% monotherapy than for the comparator if the latter rate is higher. The AETOXGR will be used to assess toxicity rates.

These will be tested using ordinal logistic regression model and model-based estimates of the difference between treatments. Odds ratio with corresponding CIs and p-values will be provided. Covariate variables such as treatment, age and sex will be included.

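### The adverse-event hypothesis lies outside the SAP's multiplicity rule: two unadjusted 0.05 tests carry a pre-stated directional conclusion that does not depend on the primary result

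*SAP*

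**What the plan says.** SAP 7.1.7 opens with "Three hypotheses are specified in the Protocol, one primary and two secondary hypotheses". The two secondary hypotheses, in protocol 2.3 and SAP 3.4, are fewer AEs (toxicity in particular) and shorter time to cure.

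For time-to-resolution, 7.1.7 gives a rule under which a positive finding is declared: "if the sum of the p-value for the primary variable and the p-value from the time-to-resolution analysis is less than the specified overall significant level". No number is attached to that level. The AE hypothesis is not mentioned, and the section ends: "Hypotheses tested for other secondary variables will all be analysed using significance elves of 0.05".

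SAP 7.10.2 turns the AE hypothesis into two nulls. One is "Hypothesis: Rate of AEs is equal in the PHMB 0.08% monotherapy is equal to that of the comparator"; the other says the same for toxicity-related AEs. The consequence is then stated: "If these are rejected, the conclusion is that the rates are different, and less with PHMB 0.08% monotherapy than for the comparator", with the qualifier that this direction applies when the comparator's rate is the higher one. There is no order, no division of alpha and no condition on CRR_12.

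Two values could serve as the overall level. SAP 5.1 sizes the trial for "power to detect superiority, with 2-sided alpha=0.10 (or equivalently 1-sided alpha=0.05". SAP 7.1.1 sets the default: "Significance tests will be two-sided and performed at the 5% significance level, unless stated otherwise".

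Two softening statements exist:
- SAP 7.9.3: "Other analyses of secondary efficacy variables will be done on a hypothesis-generating basis, i.e. no p-value adjustments will be conducted". This is limited to efficacy variables.
- A statement that all results are descriptive and that p-values only flag variables for attention. It stands with the laboratory tests in SAP 6.3.2, SAP 7.10.3 and protocol 7.5.2. In the protocol synopsis it follows the AE and laboratory paragraphs under a single Safety heading.

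**The concern.** The SAP counts the AE hypothesis among the three it lists under multiplicity, then leaves it out of the rule. A trial that met neither superiority nor non-inferiority on CRR_12 could still, on the SAP's own wording, conclude that AEs, or toxicity-related AEs, are fewer with 0.08% PHMB.

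Unadjusted safety p-values are ordinary when they are descriptive. Here the plan pre-states a favourable conclusion from them. If the synopsis wording is read to cover AEs, the protocol calls the same tests descriptive and the two documents disagree. What the trial may claim about tolerability would then be argued after the results are known.

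**Working it through.** **1. The level behind the sample size.** The inputs are in SAP 5.1 and protocol 7.6: control 67% or 63%, difference 0.20, power 80%, two-sided alpha 0.10, 10% loss. With unpooled variance, n per arm = [p1(1-p1) + p2(1-p2)] × (1.645 + 0.842)² / 0.20².

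- 67% v 87%: (0.2211 + 0.1131) × 6.18 / 0.04 = 51.7, so 52 per arm, 104 in total; 104/0.9 = 115.6, giving 116 as stated.
- 63% v 83%: (0.2331 + 0.1411) × 6.18 / 0.04 = 57.8, so 58 per arm, 116 in total, which matches the stated 116 evaluable; 116/0.9 = 128.9, giving 129 against the stated 130.

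Two-sided 0.05 would need 132 and 148 before loss. The sample size therefore rests on 0.10. This does not make 0.10 a family-wise target, and the documents do not call it one.

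**2. The sum rule adds no error.** If p1 + p2 < 0.10, then p1 < 0.10. Any false time-to-resolution claim thus comes with a primary rejection, and the pair stays at 0.100. A simulation of 2 million draws gave 0.100 at correlations 0, 0.5 and 0.8.

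**3. Adding the two AE tests.** Assume no true differences and AE tests independent of the efficacy tests. Let A be the chance that at least one AE test is rejected at two-sided 0.05; the chance that both are is then B = 0.10 - A. The overall chance of a false rejection is 1 - (1 - level)(1 - A) if either AE rejection suffices, and 1 - (1 - level)(1 - B) if both are needed. The documents give no correlation between the AE tests, so a range is shown.

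| AE-AE correlation | A | B | Either, level 0.10 | Either, level 0.05 | Both, level 0.10 | Both, level 0.05 |
|---|---|---|---|---|---|---|
| 0 | 0.0975 | 0.0025 | 18.8% | 14.3% | 10.2% | 5.2% |
| 0.5 | 0.0907 | 0.0093 | 18.2% | 13.6% | 10.8% | 5.9% |
| 0.9 | 0.0704 | 0.0296 | 16.3% | 11.7% | 12.7% | 7.8% |
| 1 | 0.0500 | 0.0500 | 14.5% | 9.75% | 14.5% | 9.75% |

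For example, the first row at level 0.10 is 1 - 0.90 × 0.95² = 0.188. Whatever the correlations, the either-suffices figure at 0.10 cannot exceed 0.10 + 0.05 + 0.05 = 20%.

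**4. Dependence between AE and efficacy tests.** This lowers the figures. At level 0.10 with either rejection sufficing, simulation gave 17.2% for AE-AE correlation 0.5 and AE-primary 0.4, and 15.1% for AE-AE 0.9 and AE-efficacy 0.5.

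**5. Only errors favouring 0.08% PHMB.** At the 0.10 level each two-sided test contributes half its alpha. Independent AE tests: 1 - 0.95 × 0.975² = 9.7%. Identical AE tests: 1 - 0.95 × 0.975 = 7.4%. The primary alone is 5%.

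**The case against.** **No family-wise promise is broken.** A reader might infer that the plan guarantees 10% over its three hypotheses and in fact runs at 17-18%. The documents support neither half. SAP 7.1.7 names an overall level without a number, 0.10 comes from the sample-size text, and the SAP default is 5%. The 17-18% needs AE tests correlated at about 0.55 to 0.8 and independent of the primary. Toxicity-related AEs are part of all AEs, so a higher correlation, and a lower figure, is plausible. This objection stands, and only ranges should be quoted.

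**The conclusion may need both rejections.** SAP 7.10.2 uses a plural after listing two nulls. On that reading there are not two separate chances of a false claim, and the inflation is smaller. The text is ambiguous, so both readings belong in the estimate. Neither makes the conclusion depend on the primary.

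**AEs may already be descriptive.** The synopsis wording can be read to cover them, and a flat 0.05 does not by itself show confirmatory intent, since it also governs efficacy variables that 7.9.3 calls hypothesis-generating. A reader might equally infer that AE testing is confirmatory beyond doubt; the documents do not settle that. But if the synopsis covers AEs, it contradicts the conclusion in 7.10.2, and the two still need reconciling.

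**Placing AEs last, behind time-to-cure, would be a poor remedy.** This is correct. The primary hypothesis can be met by non-inferiority alone. Superiority then failed, so p1 is at least the overall level, p1 + p2 cannot fall below it, and time-to-cure can never be declared. A gate there would block a tolerability claim even after the primary hypothesis was met.

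**Tolerability is not the stated rationale.** Protocol 1.2 and 5.5 argue from corneal penetration and fewer treatment failures. That is so, but the protocol still makes fewer AEs a named hypothesis.

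**Conclusion.** The structural point holds. One of three named hypotheses is left out of the multiplicity rule, split into two tests at unadjusted 0.05, and given a pre-stated directional conclusion that is independent of CRR_12.

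The size depends on which level applies and how 7.10.2 is read. At two-sided 0.10 the chance of at least one false rejection is about 15-19% if either AE rejection suffices and about 10-14.5% if both are needed. At 0.05 it is about 10-14% and 5-10%. Errors favouring 0.08% PHMB alone run at about 7-10% against 5% at the 0.10 level. These figures assume no true differences anywhere and AE tests that are independent to identical; stronger dependence on the efficacy tests lowers them.

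The primary analysis is not affected. This is a low-cost correction to what may be concluded about AEs.

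**What to change.** 1. In SAP 7.1.7, give the overall level as a number with its sidedness, reconciling 5.1 with 7.1.1.
2. In 7.1.7 and 7.10.2, label both AE p-values nominal and descriptive, as is done for the laboratory tests. Replace the sentence drawing a conclusion from rejection with reporting of estimates and confidence intervals and no formal claim. This also removes any conflict with the synopsis.
3. If the sponsor wants a formal tolerability claim, test toxicity-related AEs only after the primary hypothesis is met, by superiority or non-inferiority, and all AEs only if that test is rejected. Do not gate on time-to-cure. The AE test must fit within the stated overall level, shared with time-to-cure. The gate alone does not secure this: with equal cure rates non-inferiority is true and the gate can open, so the SAP should state the shares so that the superiority, time-to-cure and AE tests together stay within the level.

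The change takes a few sentences before the code is broken, with no new data or patients. The descriptive option gives up any formal tolerability claim. The hierarchical option gives it up when the primary is not met, and sharing the level costs some power. AE estimates and confidence intervals are reported either way.
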